6.10.5.10. Acute Renal Events

A listing of subjects with acute renal events (search criteria provided in Appendix 1) will be provided.

Severe/serious acute renal events will be considered as AESI.

6.10.5.11. Major Depressive Disorder/Suicidal Ideation Monitoring Using the C-SSRS and PHQ-9 Questionnaires

Only *serious* AEs elicited through the Columbia-Suicide Severity Rating Scale (C-SSRS), or Patient Health Questionnaire (PHQ-9) are to be recorded as AEs via the eCRF and reported to Lilly or its designee within 24 hours as SAEs.

The serious/severe major depressive disorder/suicidal ideation or behavior will be considered as AESI. Adverse events will be searched using MedDRA PT terms. Detailed searching criteria can be found in Appendix 1.

6.10.5.11.1. Patient Health Questionnaire

The PHQ-9 is a validated self-report screening tool that assesses the presence and intensity of depressive symptoms. The PHQ-9 which includes 9 questions (corresponding to 9 Diagnostic and Statistical Manual-IV depression criteria) was developed for use in primary care settings (Kroenke et al. 2001).

These items are scored in the following 4-point Likert scale: 0 = Not at all, 1 = Several days, 2 = More than half the days, and 3 = Nearly every day. Total score for the PHQ-9 ranges from 0 to 27. Greater scores denote higher level of depression.

For each subject, total scores of nonmissing items in PHQ-9 are calculated and categorized as

- none (not depressed): 0 through 4
- mild depression: 5 through 9
- moderate depression: 10 through 14

- moderately severe depression: 15 through 19
- severe depression: 20 through 27

Note: The last question "If you checked off any problems, how difficult have these problems made it for you to do your work, take care of things at home, or get along with other people?" is not included as one of these 9 questions to calculate total score.

PHQ-9 is administered at screening (baseline), Day 50 (Week 8, Visit 10), Day 106 (Week 16, Visit 18), and follow-up/early termination visit. A listing of patients with treatment-emergent depression (ie any increase in PHQ-9 categories) will be provided. The count and percentage of patients within each above category will be summarized by treatment and by visit.

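### The PHQ-9 total sums only the answered items, so on an incomplete form each blank scores zero and the depression category can only stay the same or fall; the absolute effect should be small

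*SAP*

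**What the plan says.** SAP 6.10.5.11.1 describes the instrument ("The PHQ-9 which includes 9 questions"), its item scale ("0 = Not at all, 1 = Several days, 2 = More than half the days, and 3 = Nearly every day") and its span ("Total score for the PHQ-9 ranges from 0 to 27"). The scoring rule is: "For each subject, total scores of nonmissing items in PHQ-9 are calculated and categorized as" five bands, from "none (not depressed): 0 through 4" up to "severe depression: 20 through 27", with steps at 5, 10, 15 and 20. The separate question on how difficult the problems have made daily life is left out of the total.

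The category is used twice. One use is a table: "The count and percentage of patients within each above category will be summarized by treatment and by visit". The other is a listing: "A listing of patients with treatment-emergent depression (ie any increase in PHQ-9 categories) will be provided". The form is given at screening (the baseline), Day 50, Day 106 and follow-up or early termination.

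The section sets no minimum number of answered items, no prorating and no rule making an incomplete form missing. Neither SAP 6.2 nor Protocol 9.2.2.11 supplies one. For the two food questionnaires (SAP 6.9.2.3) the SAP instead averages the nonmissing items, which does not pull an incomplete form downward.

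**The concern.** Fixed cut-points on a sum work only if every form has the same number of items. If blanks drop out of the sum and the cut-points stay put, each blank is treated as a report of no symptom. This is a rule the SAP states, so it cannot be read as silence that ordinary practice would fill.

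Treatment-emergent depression assessed by PHQ-9 is a listed safety endpoint, under the exploratory objectives. It is defined by any rise in category, so one lost point at a cut-point can decide whether a subject is listed. Protocol 9.2.2.11 has nonserious events found through the questionnaire analysed separately, with only serious ones going to the adverse event form. The PHQ-9 table and listing therefore carry part of the nonserious signal. With about 28 subjects per arm (56 randomized 1:1), one misclassified subject moves a percentage by 1/28 = 3.6 points.

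**Working it through.** **1. The plan's own figures.** Nine items scored 0 to 3 give a range of 9 × 0 = 0 to 9 × 3 = 27, as stated. The bands 0–4, 5–9, 10–14, 15–19 and 20–27 cover each integer from 0 to 27 exactly once. The scale is sound for complete forms.

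**2. Ceiling with k blanks.** The largest sum is 27 − 3k.

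| Blanks | Highest total | Highest category reachable |
|---|---|---|
| 0 | 27 | severe |
| 1 | 24 | severe |
| 2 | 21 | severe |
| 3 | 18 | moderately severe |
| 4 | 15 | moderately severe |
| 5 | 12 | moderate |

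**3. Direction at a visit.** No item is negative, so a sum over fewer items cannot exceed the full sum. Example: a true total of 10 (moderate) with one unanswered item worth 1 is scored 9 (mild).

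**4. Direction for the listing.** The listing compares a visit with screening. A blank after baseline can hide a rise; a blank at screening can lower the baseline and create a false rise. This output can err either way.

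**5. Size on affected forms (assumed).** The documents give no item-level data. The illustration uses beta-binomial items with mean item score 0.2 to 0.5, concentration 2 to 8, blanks unrelated to the answer, and totals below 15 to reflect exclusion criterion 25. The sum rule lowers the category on about 2–8% of forms with one blank and about 5–17% with two. These are shares of incomplete forms, not of all forms. If subjects skip items on which they would score high, the shares would be larger.

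**6. Prorating.** Prorated total = (sum of answered items / number answered) × 9. In the example in step 3, 9/8 × 9 = 10.125, which restores the moderate category. If the blank was truly 0, the true total is 9 and the same 10.125 is one category too high, so prorating adds some upward error. Rounding matters: a sum of 4 over eight items gives 4.5, which rounds up into the mild band but stays below 5 unrounded.

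Total misclassification at mean item score 0.35, concentration 4, totals below 15:

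| Rule | One blank | Two blanks |
|---|---|---|
| SAP sum | 4.9% (all downward) | 10.1% (all downward) |
| Prorated, rounded | 5.9% (1.1% down, 4.8% up) | 6.4% |
| Prorated, unrounded | 4.2% | 6.4% |

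Rounded prorating is no better than the SAP rule for one blank at low scores. Unrounded prorating is modestly better for one blank and clearly better for two. With one blank it leaves the 4/5 boundary where the SAP sum puts it, because 4.5 is still below 5.

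**The case against.** The strongest reply is that little is at stake. An error needs both a blank and a lost score that crosses a cut-point. At most 56 × 4 = 224 forms are scheduled, at a single center with site staff administering the questionnaires. The output is a listing and counts with no test. Special-interest status for depression rests on severe or serious events found by preferred-term search (SAP 6.10.5.11), C-SSRS monitors suicidality separately at more visits, and the primary sleep metabolic rate analysis is untouched. All of this stands and limits the point.

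A false case from a blank at screening is also less likely than a missed one. A screening score of 15 or more excludes the subject, so the site must score that form before entry.

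A reader might infer that PHQ-9 depression will be under-reported across the trial, or that a quarter to a half of categories would be wrong. The documents support neither. They give no item-missing rate. Shares as high as 25% with one blank and 53% with two arise only at an assumed mean item score of 1.5, a mean total of 9 × 1.5 = 13.5. In that setting 43–46% of forms would total 15 or more, which entry excludes. Scores can rise after baseline, so the entry limit does not bind every visit, but it makes that setting a poor guide. Nor do the documents show blanks differing by arm, so no bias in favour of tirzepatide can be read from the rule.

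The SAP sum also has one merit: it is a guaranteed lower bound. Six answered items summing to 15 put a subject at moderately severe or worse whatever the blanks hold. A blanket set-to-missing rule would lose that case, so the fix must keep it.

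**Conclusion.** The point holds as a minor scoring defect. The downward direction at each visit, and the loss of the top band with three or more blanks, follow from arithmetic and need no assumption. The frequency of the error cannot be computed from the documents. The figures of about 2–8% with one blank and 5–17% with two are conditional on a form being incomplete and rest on the assumed item model in step 5. Blanks should be rare under site administration, so the expected number of misclassified subjects is small, and no inferential result depends on it. The change is worth making because it costs almost nothing and brings PHQ-9 into line with the averaging the SAP already uses for its food questionnaires.

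**What to change.** Replace the scoring sentence in SAP 6.10.5.11.1 with a rule along these lines:

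- All nine items answered: sum them, as now.
- One or two items missing: total = (sum of answered items / number answered) × 9, with the unrounded value compared with the cut-points 5, 10, 15 and 20.
- Three or more missing: set the total and category to missing in the by-visit table and list the form. Still flag treatment-emergent depression if the baseline form is complete and the sum of answered items alone already falls in a higher category.

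The cost is a short SAP edit and one scoring line. Prorating can move a few forms up a category and so create an occasional false increase. The limit of two missing items is a convention not taken from the documents; another stated minimum would also serve. A few forms may end with no category. If every form is complete, nothing changes.

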6.10.5.11.2. Suicidal Ideation and Behavior Solicited Through C-SSRS

C-SSRS is administered at screening, Day -5 (lead-in, baseline), Day 22 (Week 4, Visit 6), Day 50 (Week 8, Visit 10), Day 78 (Week 12, Visit 14), Day 106 (Week 16, Visit 18), and follow-up/early termination visit.

The suicidal ideation, suicidal behavior, and non-suicidal self-injurious behavior are determined*:

- Suicidal ideation (5): A "yes" answer at any time during study to any 1 of the 5 suicidal ideation questions (1 "wish to dead", 2 "non-specific active suicidal thoughts", 3 "active suicidal ideation with any methods (not plan) without intent to act", 4 "active suicidal ideation with some intent to act, without specific plan", 5 "active suicidal ideation with specific plan and intent") on the C-SSRS.
- Suicidal behavior (6): A "yes" answer at any time during study to any 1 of the 5 suicidal behavior questions (6 "actual attempt", 8 "interrupted attempt", 9 "aborted attempt", 10 "preparatory acts or behavior", 11 "suicidal behavior" 12 "completed suicide") on the C-SSRS.
- Non-suicidal self-injurious behavior (1): A "yes" answer to 7 "has subject engaged in Non-Suicidal Self-Injurious behavior?"

Note: At screening and lead in visit (Day -5), C-SSRS baseline/screening version will be used, and the ideation and behavior will be assessed per subject answers on "past 1 month." At postbaseline visits, C-SSRS since last visit version will be used, and the ideation and behavior will be assessed per subject answers on "since last visit."

Baseline C-SSRS is administered at lead in visit (Day -5).

A listing of subjects with any treatment-emergent suicidal ideation, suicidal behavior, or non-suicidal self-injurious behavior during the study based on C-SSRS will be provided. The category of suicidal ideation, suicidal behavior, or non-suicidal self-injurious behavior is reported in listing. Data from C-SSRS of all visits are displayed for these subjects.

If any data were collected from self-harm supplemental and self-harm follow-up questionnaires (single CRF) which are triggered by any self-harm through C-SSRS, it will be listed.

6.10.7. Electrocardiogram

Electrocardiograms (ECGs) will be performed for safety monitoring purposes only. Any clinically significant ECG findings entered as AEs will be included in AE summaries.

6.10.8. Safety Laboratory Parameters

All laboratory data will be reported in the International System of Units and conventional units.

Descriptive summaries of clinical chemistry, hematology, and endocrine (calcitonin) data and their changes from baseline will be provided at each visit by treatment.

Additionally, clinical chemistry, hematology, urinalysis, and endocrine (calcitonin) data outside the reference ranges will be listed.

If any safety lab measurements are (1) below the quantification limit (eg <QL), $\frac{1}{2}$ \times QL may be used for the calculation of summary statistics; (2) above the quantification limit (eg >QL), 1.1 \times QL may be used for the calculation of summary statistics, if deemed appropriate.

6.11. Evaluation of Immunogenicity

Baseline immunogenicity sample is collected on Day 1 pre-dose.

For TE-ADA+ subjects, the distribution of maximum titers may be described.

The frequency and percentage of patients with preexisting ADA and with TE-ADA+ to tirzepatide may be tabulated.

If cross-reactive antibodies to native GIP and GLP-1, or neutralizing antibodies against native GLP-1 and GIP assays are performed, the frequency and percentage of each may be tabulated.

A listing will be provided of immunogenicity assessments. This includes the tirzepatide concentration from a simultaneous pharmacokinetic sample and the clinical interpretation result (ADA Present, ADA Not Present, ADA Inconclusive, or Missing). A listing of TEAE for patients with TE ADA+ or Injection Site Reaction or Potential Hypersensitivity may be provided.

Cases of TE-ADA that are associated with AEs of either severe/serious hypersensitivity or severe/serious injection site reaction will be classified as AESI.

6.12. Interim Analyses

No interim analyses are planned for this study. If an unplanned interim analysis is deemed necessary, the Lilly clinical pharmacologist, clinical research scientist/clinical research physician, investigator, or designee will consult with the appropriate medical director or designee to determine if it is necessary to amend the protocol.

6.13. COVID-19 Impact Assessment

A listing of subjects with adverse events related to COVID-19, including death due to COVID-19, serious COVID-19 adverse events, and COVID-19 adverse events, may be provided. Protocol deviations that study disruptions related to COVID-19 may be described in CSR.

7. Unblinding Plan

The blinding/unblinding plan is not part of this SAP. The approved blinding/unblinding plan is stored in Leo.

8. Changes from the Protocol Specified Statistical Analyses

Changes from the protocol specified statistical analyses are as follows:

- In protocol Section 1 and Section 10.3.3.2, it states "The primary analysis will be performed in all randomized subjects with evaluable data (modified intent-to-treat [mITT] population)". It is clarified in this SAP that PD analyses will be conducted on the PD analysis set (ie evaluable data from all randomized subjects who are exposed at least 1 dose of study drug). This is consistent with protocol Section 10.3 "Pharmacodynamic analyses will be conducted on data from all subjects who receive at least 1 dose of the IP and have evaluable data."
- In protocol Section 10.1 Sample Size Determination, it is updated to "Up to 56 subjects are planned to be randomized so that approximately 46 subjects complete the study assuming 15% discontinuation rate. These 56 subjects will be randomized to QW tirzepatide or placebo in a 1:1 ratio. The estimated standard deviation of the change in SMR from baseline is 117 kcal/day (Heilbronn et al. 2006). With an expected treatment difference of 100 kcal/day, this provides at least 80% power for the comparison of tirzepatide versus placebo based on 2 sample t-test using 2-sided test at alpha level of 0.05 for the assessment of the primary endpoint."
- In protocol appendix Section 6.4, it states "The Food Preference Questionnaires (FPQ) (Geiselman et al. 1998) assesses preferences for 72 foods in a 2 (high-fat, low-fat) by 3 (high-simple sugar, high-complex carbohydrate, low-carbohydrate/high-protein) matrix". It is updated and clarified in this SAP "The macronutrient self-selection paradigm (MSSP) is an instrument that has to be updated very frequently because of food availability in the grocery stores. During the updates, in the current version of FPQ used in CRF for this study contains 73 food items (where 13 food items in low fat/high sugar category)."
- In protocol Section 7.6 Treatment Compliance, it states "Subjects will be considered compliant if they received at least 75% of their scheduled doses for each dosing interval (Weeks 1 to 2, Weeks 3 to 4, Weeks 5 to 8, and Weeks 9 to endpoint) during the treatment period." This is updated in SAP that subjects will be considered treatment compliant if taking ≥75% of their scheduled doses for 18-week treatment period taking into account early termination (specifically excluding the period after early termination), for statistical summaries.

9. References

- Frayn, KN. Calculation of substrate oxidation rates in vivo from gaseous exchange. *J Appl Physiol Respir Environ Exerc Physiol*. 1983;55(2):628-634. https://doi.org/10.1152/jappl.1983.55.2.628
- Heilbronn LK, de Jonge L, Frisard MI, et al. Effect of 6-month calorie restriction on biomarkers of longevity, metabolic adaptation, and oxidative stress in overweight individuals: a randomized controlled trial. *JAMA*. 2006;295(13):1539-1548. https://doi.org/10.1001/jama.295.13.1539
